4.1.4.1 BI 836826 infusion rates

Table 4.1.4.1: 1 provides a summary of planned and modified infusion rates. Pre-medication prior to each administration of BI 836826 is required [Section 4.2.1.2.1](#)

Table 4.1.4.1:1 Planned and modified infusion rates

Day of Treatment	Dose of BI 836826	Initial Rate of Infusion and Maximum Escalation Steps*	Maximum Allowed Infusion Duration	Maximum Allowed Infusion Rate
Cycle 1 Day 1	10 mg	2 mg/hr x 60 min Escalate by 1 mg/hr every 30 min as tolerated to maximum allowed rate**	24 hr	5 mg/hr
Cycle 1 Day 2	50% of target dose	≤ 50 mg/hr x 60 min Escalate by ≤ 50 mg/hr every 30 min as tolerated to maximum allowed rate**	24 hr	400 mg/hr
Cycle 1 Day 8	50% of target dose	≤ 50 mg/hr x 60 min Escalate by ≤ 50 mg/hr every 30 min as tolerated to maximum allowed rate**	24 hr	400 mg/hr
Cycle 1 Day 15	100% of target dose	≤ 50 mg/hr x 60 min Escalate by ≤ 50 mg/hr every 30 min as tolerated to maximum allowed rate**	24 hr	400 mg/hr
Cycle 2 Day 1 and subsequent Cycles	100% of target dose	≤ 50 mg/hr x 30 min, then ≤ 100 mg/hr x 30 min Escalate by ≤ 100 mg/hr as tolerated to maximum allowed rate**	24 hr	500 mg/hr

* Infusion rates may be adjusted and given extremely slowly over a longer period of time (not to exceed 24 hours) for patients with a White Blood Cell Count (WBC) ≥ 100 x 10⁹/L at the time of infusion,

** slower start rate or smaller increments allowed at investigator's discretion

Cycle 1 Day 1: BI 836826 “pre-dose” of 10 mg:

BI 836826 administration will start with a “pre-dose” of 10 mg on Day 1 of the first cycle. Pre-medication according to [Section 4.2.1.2.1](#) is mandatory. The initial infusion rate to mitigate the risk for severe infusion related reactions is 2 mg/h for the first 60 minutes. In the absence of infusion related reactions the rate can be escalated every 30 minutes by increments of 1 mg/h to a maximum rate of 5 mg/h.

In patients with a high risk for IRRs or TLS (e.g., a $WBC \geq 100 \times 10^9/L$ at the start of infusion), or occurrence of an IRR during the infusion, the infusion may be given extremely slowly over a longer period of time, but not exceeding 24 hours.

Cycle 1 Day 2 and Cycle 1 Day 8: BI 836826 at 50% of target dose:

Pre-medication, according to [Section 4.2.1.2.1](#), is mandatory. The recommended initial infusion rate to mitigate the risk for severe IRRs should not exceed 50 mg/h for the first 60 minutes. The rate can be escalated every 30 minutes by increments of 50 mg/h or less to a maximum rate of 400 mg/h in the absence of IRRs. A slower start rate or smaller increments are possible based on individual risk assessment. Reductions in the infusion rate may be applied as indicated to ensure tolerability. In patients with a high risk for IRRs or TLS (e.g., a white blood cell count (WBC) $\geq 100 \times 10^9/L$ at the start of infusion), or occurrence of an IRR during the infusion, the infusion may be given extremely slowly over a longer period of time but not exceeding 24 hours.

Cycle 1 Day 15: BI 836826 at 100% of target dose:

Pre-medication, according to [Section 4.2.1.2.1](#), is mandatory. The recommended initial infusion rate to mitigate the risk for severe IRRs should not exceed 50 mg/h for the first 60 minutes. The rate can be escalated every 30 minutes by increments of 50 mg/h or less to a maximum rate of 400 mg/h in the absence of IRRs. A slower start rate or smaller increments are possible based on individual risk assessment. Reductions in the infusion rate may be applied as indicated to ensure tolerability. In patients with a high risk for IRRs or TLS (e.g., a $WBC \geq 100 \times 10^9/L$ at the start of infusion), or occurrence of an IRR during the infusion, the infusion may be given extremely slowly over a longer period of time but not exceeding 24 hours.

Cycle 2 Day 1 and subsequent cycles: BI 836826 at 100% of target dose:

In the absence of infusion related reactions during the administration of the previous full dose, the subsequent administration of BI 836826 is recommended to start at a rate of 50 mg/h or less for the first 30 minutes, followed by a rate of 100 mg/h or less for 30 minutes. Incremental steps thereafter may be larger depending on individual tolerability, but must not exceed 100 mg/h. A maximum rate of 500 mg/h is not to be exceeded. A slower start rate and smaller increments are possible based on individual risk. Reductions in the infusion rate may be applied as indicated to ensure tolerability. Pre-medication should be considered according to [Section 4.2.1.2.1](#).

4.1.4.2 Management of infusion related reactions

IRRs are events that are directly related to antibody–antigen interactions and have been also characterized as cytokine-release syndromes that result from the interaction of antibody with antigen on circulating hematopoietic cells [[R14-4170](#)]. Symptoms are often difficult to distinguish from anaphylactoid or hypersensitivity reactions. IRRs will be captured as an AE on the dedicated IRR eCRF page together with the clinically most important symptoms. Cytokine-release syndrome should be reported under the term IRR, while a true allergic IgE mediated hypersensitivity reaction should be reported on the regular AE page.

Hospitalization and overnight surveillance should be considered by the investigator for patients at high risk for TLS in Cycle 1 on Day 2 following the first infusion of BI 836826 at

50% of the assigned dose. Surveillance of the patient during and until at least 2 hours after the end of each BI 836826 infusion in Cycle 1 is required. Mandatory surveillance can be reduced to at least 1 hour in Cycle 2 and subsequent Cycles if no AE which would necessitate longer observation as per investigator's judgement occurs during the infusion or the 1 hour surveillance period. Surveillance should be prolonged as clinically indicated to monitor or treat AEs.

During the infusion and surveillance period, appropriate monitoring of vital signs is recommended, and access to emergency care should be available.

In case an IRR is observed, appropriate measures depending on the type and severity of the reaction should be taken by the investigator according to best medical judgment and local guidelines. Supportive therapy for symptoms of IRRs may be administered at the investigator's discretion as indicated. Additional glucocorticoids should be considered in particular in patients with Grade 3 or 4 reactions or potentially life threatening symptoms, e.g. bronchospasm.

If symptoms of an IRR occur while BI 836826 is administered, the following instructions and tabular summary of procedures for rate changes and interruptions of BI 836826 must be followed:

Table 4.1.4.2: 1 BI 836826 management of infusion-related reactions

NCI CTCAE Grade of IRR	Action	Continuing BI 836826*	
Grade 1	Reduce infusion rate to 50% of the rate at which symptoms occurred; infusion may be interrupted at investigator's discretion	After resolution of symptoms	Increase infusion rate to the rate at which the reaction occurred
Grade 2	Interrupt infusion	After resolution of symptoms	Resume infusion at a slower rate than that at which the reaction occurred
Grade 3	Interrupt infusion	After resolution of symptoms	Resume infusion at \leq 50% of the rate at which the reaction occurred x 30 minutes
Grade 4	Stop infusion	Do not re-expose	

- *Once subject is stable after reintroduction of initial infusion rate, proceed per [Section 4.1.4.1](#), Dosage and Administration of BI 836826
- In the case of an infusion-related reaction of CTCAE Grade 1, the infusion rate of BI 836826 should be reduced to 50% of the previous rate, but may also be interrupted. Upon resolution of symptoms, the infusion may be resumed at an infusion rate not higher

than the rate at which the IRR occurred, and escalated at the investigator's discretion within the limits described above.

- In the case of an infusion-related reaction of CTCAE Grade 2, the infusion of BI 836826 should be interrupted. Supportive treatment may be administered as indicated. Upon resolution of symptoms, the infusion may be resumed at 50% of the previous infusion rate and infusion rate escalated at the investigator's discretion within the limits described above.
- In the case of an infusion-related reaction of CTCAE Grade 3, the infusion with BI 836826 has to be stopped immediately. Supportive therapy is typically indicated, glucocorticoids should be considered for management. Once all symptoms have resolved, administration of BI 836826 may be resumed for at least 30 minutes at a rate which should not exceed 50% of the rate at which the reaction occurred. Re-increase of the infusion rate as tolerated by the subject is possible within the limits described above.
- In the case of an IRR reaction of CTCAE Grade 4, the infusion has to be stopped immediately. Symptoms should be aggressively treated, glucocorticoids should be considered for management. Re-exposure after the event is not permitted.

Changes of the infusion rate and temporary interruptions of the infusion have to be recorded in the eCRF.

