4.1.3 Selection of doses in the trial

The starting dose of BI 836826 for this trial was selected on data from trial 1270.1, the first in human, dose escalation trial of BI 836826 in CLL. A dose of 400 mg was found to be safe in 1270.1. The first dose tier of BI 836826 to be tested in combination with ibrutinib will be BI 836826 100 mg. A dose of 100 mg includes a safety margin for the combination, and was found to be moderately clinically active.

Based on the Bayesian model in [Section 7.1](#), the dose combination 100mg BI 836826 and 420mg ibrutinib has a prior probability of overdosing below 25%; it fulfills the overdose criterion and is therefore a suitable starting dose combination (see [Section 7.1](#)).

The dose is planned to be escalated in dose tiers recommended by the BLRM. A maximum escalation step of 100% will be allowed. The provisional dose levels are 100 mg, 200 mg, 400 mg, 600 mg, 800 mg, and 1400 mg of BI 836826, unless recommended differently by the BLRM/SRC. Intermediate or lower dose levels, depending on the number of DLTs observed

in the study may be investigated if agreed upon by the SRC. Intra-patient dose-escalation of BI 836826 will not be allowed in this trial.

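### After a Grade 2 infusion reaction, Table 4.1.4.2:1 allows restart at any slower rate, while the equally binding text in Section 4.1.4.2 says 50%

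*Protocol*

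**What the plan says.** Protocol Section 4.1.4.2 gives the rules for an IRR during a BI 836826 infusion twice, once in Table 4.1.4.2:1 and once in bullets below it. The lead-in states that the "instructions and tabular summary of procedures for rate changes and interruptions of BI 836826 must be followed". It gives no order of precedence.

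For Grade 2, both places require the infusion to be interrupted and the symptoms to resolve. They then differ on the restart:

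- Table: "Resume infusion at a slower rate than that at which the reaction occurred".
- Bullet: "the infusion may be resumed at 50% of the previous infusion rate", after which the investigator may escalate within the stated limits.

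For Grade 3, the bullet allows restart for at least 30 minutes "at a rate which should not exceed 50% of the rate at which the reaction occurred", and the table row agrees. For Grade 4, the table forbids re-exposure and the bullet repeats it: "Re-exposure after the event is not permitted".

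**The concern.** Two limits stand under one mandatory lead-in. A site that works from the table at the bedside may restart just below the rate that provoked the reaction. A site that works from the bullet halves it.

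Infusion rate is one of the protocol's main controls for this risk. Section 1.2.1 reports that in trial 1270.1 the schedule was slowed and the first dose split because of reactions of at most Grade 2. The note in Section 2.1 stops recruitment but lets current patients complete treatment per protocol, so the rule is still in use.

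A lesser consequence is in reporting. SAP Table 6.2:1 (code C1) and SAP Section 7.3 depend on whether the infusion schedule was followed, and two sites could answer differently for the same restart. C1 excludes no patient from any analysis.

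**Working it through.** **1. The two sources side by side (Section 4.1.4.2)**

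| IRR grade | Table 4.1.4.2:1 | Bullet | Same limit? |
|---|---|---|---|
| 1 | Reduce to 50%; interruption optional | Reduce to 50%; interruption optional | Yes |
| 2 | Interrupt; restart at any rate below the reaction rate | Interrupt; restart at 50% | **No** |
| 3 | Interrupt; restart at ≤50% for 30 min | Stop; restart at ≤50% for at least 30 min | Yes |
| 4 | Stop; no re-exposure | Stop; no re-exposure | Yes |

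Grade 2 is the only grade where the bullet carries a 50% figure that the table lacks.

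**2. Which restarts comply**

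Let R be the rate at the reaction and r the restart rate. I take the bullet's previous rate to mean R.

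- Table: r < R.
- Bullet: r = 0.5R.
- Both: r = 0.5R.
- Table only: 0.5R < r < R. The ratio to the bullet's rate is below R / 0.5R = 2.

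A restart below 0.5R also meets the table but, read literally, not the bullet. Wording the limit as at most 50% removes that problem too.

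**3. Size at the maximum rates in Table 4.1.4.1:1**

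| Infusion | Maximum R (mg/h) | Bullet, 0.5R (mg/h) | Table |
|---|---|---|---|
| Cycle 1 Day 1 (10 mg) | 5 | 2.5 | below 5 |
| Cycle 1 Days 2, 8, 15 | 400 | 200 | below 400 |
| Cycle 2 onward | 500 | 250 | below 500 |

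**4. Whether those maxima are reached**

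Section 4.1.3 lists the tiers: "The provisional dose levels are 100 mg, 200 mg, 400 mg, 600 mg, 800 mg, and 1400 mg of BI 836826".

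*Cycle 1 Day 15.* The fastest schedule is 50 mg/h for 1 h, then "Escalate by ≤ 50 mg/hr every 30 min as tolerated to maximum allowed rate". Cumulative dose at the end of each step:

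- 50 mg/h: 50 × 1 = 50 mg
- 100 mg/h: 50 + 100 × 0.5 = 100 mg
- 150 mg/h: 100 + 75 = 175 mg
- 200 mg/h: 175 + 100 = 275 mg
- 250 mg/h: 275 + 125 = 400 mg
- 300 mg/h: 400 + 150 = 550 mg
- 350 mg/h: 550 + 175 = 725 mg
- 400 mg/h thereafter

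At 100/200/400/600/800/1400 mg the Day 15 peak is therefore 100/200/250/350/400/400 mg/h, and the bullet's restart after a reaction at peak is 50/100/125/175/200/200 mg/h. On Days 2 and 8 (half dose) the peaks are 50/100/200/250/250/350 mg/h, so 400 mg/h is not reached.

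*Cycle 2 onward.* The first hour gives 50 × 0.5 + 100 × 0.5 = 75 mg. After that the table says "Escalate by ≤ 100 mg/hr as tolerated to maximum allowed rate" and states no step interval. Assuming steps of 15, 30 or 60 minutes, the peak is:

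| Dose (mg) | 15 min | 30 min | 60 min |
|---|---|---|---|
| 100 | 200 | 200 | 200 |
| 400 | 500 | 400 | 300 |
| 800 | 500 | 500 | 400 |
| 1400 | 500 | 500 | 500 |

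(mg/h.) The absolute gap thus depends on dose, day and step length. The ratio does not.

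**5. How many patients**

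In trial 1270.1, 25 of 36 patients (69%) had an IRR and 3 had a Grade 3 reaction (Section 1.2.1). The number with Grade 2 is not given. Nor do the documents give the tier or cycle of the patients still on treatment. The number affected cannot be computed.

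**The case against.** The strongest reply is that nothing forces a breach. The table calls itself a summary, the bullet is the more specific statement, and a 50% restart satisfies both. The bullet's verb is permissive, and it lets the rate be re-escalated at the investigator's discretion without the 30-minute hold set for Grade 3. Both versions require interruption and resolution first. A milder reaction may also reasonably have a looser rule than a more severe one, and the documents do not say whether the sponsor meant the table or the bullet.

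Most of this stands, and it makes the point minor. It does not remove the mismatch: a restart at, say, 80% of the reaction rate is allowed by one mandatory source and not described by the other. The looser row, taken alone, is also no evidence of intent, since the bullet gives Grade 2 a 50% figure.

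A reader might also infer that Section 4.1.4.5 undermines the Grade 4 ban. Its row for other non-haematological events of Grade 3 or higher allows resumption, and its occurrence table restarts a first related event at the assigned dose; neither excepts IRRs. The documents do not support that reading. The ban is specific and stated twice. Section 4.1.4.5 is headed as recommendations, and its Grade 3 or higher row also allows discontinuation, so stopping complies with both. The occurrence table describes how dose reductions may be made. At most a cross-reference is missing.

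**Conclusion.** The Grade 2 rule is wrong as written: table and bullet set different restart limits under one instruction to follow both. A site using the table could restart at 51–99% of the reaction rate, up to nearly twice the bullet's rate. This assumes that the previous rate in the bullet means the rate at the reaction, and that the table has the same force as the text, as the lead-in says.

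The weight is small. Most of the absolute rates worked out here concern Cycle 1 or the higher tiers, and nothing shows that a continuing patient is there. The Cycle 2 figures rest on an assumed step interval. No harm from a faster restart is demonstrated.

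A reader might infer an effect on dose escalation. There is none through the DLT count: Section 5.3.6.2 excludes IRRs of any grade from DLT, so the model input, the MTD criterion and the endpoint analyses are untouched.

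**What to change.** In Section 4.1.4.2, write the same limit, at most 50% of the rate at which the reaction occurred, in the Grade 2 row of Table 4.1.4.2:1 and in the Grade 2 bullet. This gives Grade 2 the same starting cap as Grade 3; Grade 3 keeps its 30-minute hold. The sponsor should confirm that this is the intended rule.

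Optionally, add a line to Section 4.1.4.5 stating that IRRs are governed by Section 4.1.4.2.

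The cost is one table row and one sentence, plus one line if the option is taken. Data collection and analysis do not change.

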4.1.4.3 Ibrutinib dosing

Dosing of ibrutinib will be guided by the package insert ([R15-5127](#)). The prescribed dose of 420 mg of ibrutinib will be administered orally daily. Capsules should be taken orally with a glass of water. The capsules should not be broken, opened or chewed. Patients should be instructed not to drink grapefruit juice, eat grapefruit, or eat Seville oranges while taking ibrutinib.

If a dose of ibrutinib is not taken at the scheduled time, it can be taken as soon as possible on the same day with a return to the normal schedule the following day. Extra capsules of ibrutinib should not be taken to make up for the missed dose.

On days of BI 836826 dosing, ibrutinib will be administered in the clinic before the start of the infusion. Prior to these visits, patients should be reminded to record the time of their dose the day prior to their scheduled visit and not to take their morning dose of ibrutinib before coming into the clinic. Patients should also be reminded to bring their supply of ibrutinib to the clinic for dosing. Ibrutinib administration information, including the exact time of dose, administered in the clinic or hospital is to be recorded.

4.1.4.4 Criteria for administration of BI 836826 at 100% of the assigned dose (Cycle 1 Day 15 and Following)

Prior to each administration of full dose of BI 836826 (i.e. Cycle 1 Day 15 and subsequent administrations), AEs and CBC with differential will be assessed. To continue treatment with a further infusion of BI 836826, all of the following criteria must be met:

- Neutrophils ≥ 1000 / μ L (1.0×10^9 /L)
- Platelets ≥ 25.000 / μ L (25×10^9 /L)
- Acceptable tolerability and recovery from AEs (see [Section 4.1.4.5](#))

In case one of these criteria is not fulfilled, blood counts and/or the AE should be re-evaluated at in appropriate intervals and additional laboratory data should be captured in the eCRF.

Treatment with BI 836826 may be delayed to enable resolution of AEs, concurrent diseases, recovery from surgical procedures, or other individual reasons. Delays of the next infusion for > 4 weeks for other reasons should be discussed and agreed with the Sponsor.

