4.1.4.5 Recommendations for dose modification in response to AEs

AEs should be assessed for relatedness as outlined in [Section 5.3.6](#). In case an AE is considered related to ibrutinib, recommendations for dose modifications for ibrutinib should be considered. In case an AE is considered related to BI 836826, recommendations for dose modifications for BI 836826 should be followed. In case an AE is considered related to both ibrutinib and BI 836826, it is at the discretion of the investigator whether to modify the dose for both drugs at the same time, or only for one drug.

Dose modifications for adverse events related to ibrutinib:

Ibrutinib will be used within the approved label indication as per clinical routine. The following recommendations as per label should be considered by the investigator when administering ibrutinib:

‘Interrupt ibrutinib for

- any Grade 3 or greater non-hematological,
- Grade 3 or greater neutropenia with infection or fever, or
- Grade 4 hematological toxicities.

Once the symptoms of the toxicity have resolved to Grade 1 or baseline (recovery), ibrutinib may be reinitiated at the starting dose. If the toxicity reoccurs, reduce dose by one capsule (140 mg per day). A second reduction of dose by 140 mg may be considered as needed. If these toxicities persist or recur following two dose reductions, discontinue ibrutinib.’

Dose modifications for adverse events related to BI 836826

Worst NCI CTCAE Grade after previous dose	BI 836826
Neutrophil values at nadir after previous dose	
< LLN and $\geq 1 \times 10^9/L$	Maintain current dose level and schedule
< $1 \times 10^9/L$ and $\geq 0.5 \times 10^9/L$ or < $0.5 \times 10^9/L$ for ≤ 7 days	Monitor neutrophils until recovery. Delay BI 836826 until Grade ≤ 2 . Thereafter resume at full dose.
< $0.5 \times 10^9/L$ for >7 days	Monitor neutrophils until recovery. Delay BI 836826 until Grade ≤ 2 . Thereafter may resume at full dose. Consider G-CSF support. If neutropenia Grade 4 for > 7 days recurs despite G-CSF support in subsequent cycle, the dose of BI 836826 should be reduced to 50%.
Thrombocytopenia	
PLT > 10 000/ μ L	Maintain current dose level and schedule

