PLT $\leq 10 000/\mu$ L at two separate measurements (at least 24 hours apart)	Monitor thrombocytes until recovery to Grade 3. Consider platelet transfusion. Delay BI 836826 until Grade ≤ 3 (recovery). Upon recovery, BI 836826 may be resumed at full dose. If a level of PLT $\leq 10 000/\mu$ L, at two separate measurements at least 24 hours apart, recurs in the subsequent cycle, dose of BI 836826 should be reduced by 50%.
Hepatic Adverse Events (elevations in ALT, AST)	
Grade ≤ 1 (ALT/AST $\leq 3 \times$ ULN)	Maintain current dose level and schedule
Grade 2 (ALT/AST >3 and $\leq 5 \times$ ULN)	Delay BI 836826 until Grade ≤ 1 . Thereafter resume at full dose.
Grade 3 or 4 (ALT/AST >5 and $\leq 20 \times$ ULN)	Withhold BI 836826. Monitor ALT/AST at least 1x per week until Grade ≤ 1 . Thereafter, may resume at full dose. If ALT/AST elevation Grade ≥ 3 recurs with BI 836826 at full dose, reduce BI 836826 by 50%. Reescalation of BI 836826 upon resolution of symptoms to 100% possible at

Worst NCI CTCAE Grade after previous dose	BI 836826
	the investigator's discretion in later infusions.
Hepatic Adverse Events (elevations in bilirubin)	
Grade ≤1 (bilirubin ≤1.5 x ULN)	Maintain current dose level and schedule
Grade 2 (bilirubin >1.5 and ≤3.0 x ULN)	Delay BI 836826 until Grade ≤1. Thereafter resume at full dose.
Grade 3 or 4 (bilirubin >1.5 and ≤3.0 x ULN)	Withhold BI 836826. Monitor bilirubin at least 1x per week until Grade ≤1. Thereafter, may resume at full dose. If bilirubin elevation Grade ≥3 recurs with BI 836826 at full dose, reduce BI 836826 by 50%. Reescalation of BI 836826 upon resolution of symptoms to 100% possible at the investigator's discretion in later infusions.
Other Non-haematological Adverse Events	
Grade ≤2	Maintain current dose level and schedule
Grade ≥3	Withhold study drug until Grade ≤1. Study drug may be resumed at initial or lower dose level or discontinued at investigator's discretion.

A dose reduction of BI 836826 may be performed twice as outlined in the next table. In case an AE recurs or persists following two dose reductions, BI 836826 should be discontinued.

Occurrence of a BI 836826 related AE included in previous table	BI 836826 Dose Modification at subsequent Infusion
First	Restart at assigned dose
Second	Reduce BI 836826 by 50% at next infusion (dose level -1)
Third	Reduce dose level -1 by 50%, i.e. reduce initially assigned dose of BI 836826 by 75% at next infusion (dose level-2)
Fourth	Discontinue BI 836826

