5.3.6.2 Dose limiting toxicities

All drug related AEs, including SAEs and deaths, will be carefully evaluated by investigators for DLT. Dose escalation decisions will be based on DLTs observed in Cycle 1. Dose Limiting Toxicity is defined as follows:

- Any non-hematologic AE of Grade ≥ 3 related to BI 836826 and/or ibrutinib will be considered DLT, except:
 - Infusion-related reaction, any Grade
 - Grade 3 AST- and/or ALT elevation without concomitant bilirubin elevation or any other asymptomatic Grade 3 laboratory abnormality with spontaneous recovery within 1 week
- The following hematologic AEs related to BI 836826 and/or ibrutinib will be considered DLT:
 - Grade 4 neutropenia with concomitant infection
 - Grade 4 febrile neutropenia, and Grade 3 febrile neutropenia not resolving within 72 hours with appropriate treatment (antibiotics, antivirals, antifungals, growth factor support)
 - Grade 4 thrombocytopenia with clinically significant bleeding
 - Grade 4 anemia
 - Any Grade 5 hematologic AE

Patients will be evaluable for MTD in Cycle 1 if:

- a DLT occurs at any time, or
- a minimum exposure to BI 836826 and ibrutinib has been achieved. The minimum exposure is defined as $\geq 80\%$ of the planned ibrutinib doses (since Day 1 of Cycle 1) and all planned administrations of BI 836826 in Cycle 1. If the administration in Cycle 1 on Day 15 is delayed, the DLT evaluation will be prolonged to cover 14 days after the D15 administration.

All patients who have started trial treatment, but do not meet at least one of the above criteria at the end of Cycle 1 will be evaluated for safety, but replaced for MTD evaluation.

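### A platelet count above 10,000 and below 25,000/µL on the day of a full-dose infusion gets opposite instructions from Protocol Sections 4.1.4.4 and 4.1.4.5

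*Protocol*

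**What the plan says.** Protocol Section 4.1.4.4 covers every infusion at 100% of the assigned dose, starting with Cycle 1 Day 15. Adverse events and a blood count are checked first, and "To continue treatment with a further infusion of BI 836826, all of the following criteria must be met". The list requires neutrophils of at least 1000/µL, "Platelets ≥ 25.000" per µL (that is, 25,000/µL), and tolerability and recovery from adverse events, for which it points to Section 4.1.4.5. If a criterion fails, the count or event is re-evaluated later.

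Protocol Section 4.1.4.5 gives the actions for adverse events related to BI 836826. It is titled as recommendations, but for such events it says that "recommendations for dose modifications for BI 836826 should be followed". Its table is headed "Worst NCI CTCAE Grade after previous dose". The thrombocytopenia block has two rows:

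- Platelets above 10,000/µL: "Maintain current dose level and schedule".
- Platelets of 10,000/µL or below on two measurements at least 24 hours apart: "Monitor thrombocytes until recovery to Grade 3. Consider platelet transfusion", with BI 836826 delayed until that recovery.

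Neither section, nor any other passage, says which one takes precedence.

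**The concern.** The two sections set different platelet limits for what is, on an infusion day, the same decision. In the interval between the limits, one section withholds the infusion and the other tells the site to keep to schedule. Sites could act differently on the same count, and each could cite the protocol.

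The protocol treats low platelets as a safety matter. Section 2.3 warns that the combination may make thrombocytopenia more frequent or more severe, Section 1.2.2 lists hemorrhage among the reactions seen with ibrutinib, and Section 4.2.2.1 urges caution with anticoagulants and antiplatelet drugs below 50 x 10^9/L. Section 2.1 stops recruitment but lets current patients continue, so the rule still applies to their remaining infusions.

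There is also a possible link to the dose-finding data. Section 5.3.6.2 requires "all planned administrations of BI 836826 in Cycle 1" for a patient without a DLT to count towards the MTD, so a withheld Day 15 dose can matter there.

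**Working it through.** No power or sample-size formula applies. The check sets the two rules side by side and follows a low count through the Cycle 1 rules.

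**Step 1: the two rules by platelet count on the infusion day** (full dose, decline related to BI 836826, same value taken as the worst since the previous dose):

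| Platelets/µL | Section 4.1.4.4 | Section 4.1.4.5 | Agreement |
|---|---|---|---|
| 25,000 or more | criterion met | keep dose and schedule | yes |
| 24,999 | hold | keep dose and schedule | **no** |
| 15,000 | hold | keep dose and schedule | **no** |
| 10,001 | hold | keep dose and schedule | **no** |
| 10,000 or less | hold | delay, if seen on two measurements | no opposite instruction |

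The conflict interval is above 10,000 and below 25,000/µL.

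**Step 2: is it specific to platelets?** For neutrophils, Section 4.1.4.4 requires at least 1000/µL. The neutrophil rows of Section 4.1.4.5 keep the schedule at 1 x 10^9/L or more and delay below it. These are the same limit, so only the platelet rows depart from the gate.

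**Step 3: nadir or infusion-day value?** The table uses the worst value since the previous dose; the gate uses the count before the infusion. A nadir of 15,000 that is back to 25,000 or more on the infusion day satisfies both. The rules collide only when the count is still in the interval on that day.

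**Step 4: Cycle 1 Day 15.** Four infusions are planned in Cycle 1 (10 mg, 50%, 50%, 100%). Section 6.1 lets Day 15 slip by one week and omits the dose if longer is needed. Section 5.3.6.2 extends the DLT evaluation to 14 days after a delayed Day 15 dose. Assuming the ibrutinib exposure requirement is met and no DLT occurs:

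- Infused on Day 15 under Section 4.1.4.5: 4 of 4 infusions, evaluable at the end of Cycle 1.
- Held under Section 4.1.4.4, recovered within one week: infused by Day 15 + 7 = 22, window to about Day 22 + 14 = 36, 4 of 4 infusions, evaluable.
- Held, not recovered within one week: dose omitted, 3 of 4 infusions, not evaluable and replaced.

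A low count without clinically significant bleeding is not a DLT under Section 5.3.6.2 (fatal events apart), so it does not itself make the patient evaluable.

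**Step 5: what losing one patient does to escalation.** Table 10.7:1 gives an overdose probability at 200 mg of 0.119 after 0 DLTs in 3 patients at 100 mg, and 0.144 after 0 in 2. Both are below the 0.25 limit. Reweighting prior draws from Table 7.1:3 gives 0.117 and 0.145 with the interaction acting on dose ratios, and 0.091 and 0.117 with the interaction as printed. Losing one DLT-free patient does not by itself block that step.

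**The case against.** The strongest reply is that the sections are cumulative. Section 4.1.4.4 lists recovery under Section 4.1.4.5 as one of several conditions, so satisfying the table does not waive the platelet criterion, and mandatory wording should outrank a section titled as recommendations. On that reading every full dose in the interval is held. It is a sensible reading, but the protocol never states it. It also leaves the table telling sites to keep the schedule in a case where the schedule cannot be kept, and Section 4.1.4.5 says its recommendations are to be followed for related events.

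The second reply is that the rules use different measurements and the table covers only related events. This stands as a limit on scope: transient nadirs and unrelated declines drop out. A related count still in the interval on the infusion day remains.

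Three stronger readings are tempting, and the documents do not support them:

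- *About 4 of 20 patients will meet the conflict.* Section 1.2.1 reports drug-related Grade 3 or 4 thrombocytopenia in 8/36 = 22.2%, and 0.222 x 20 = 4.4. That counts worst grades at any time, not infusion-day counts in the interval. The same section reports recovery by Day 8 in most patients, and full doses follow the previous infusion by 7 days (Cycle 1 Day 15) or by 14 or 28 days later. With recruitment stopped, scaling to 20 is also inappropriate.
- *A single unrepeated value of 10,000/µL or below is left uncovered.* It fits neither platelet row of Section 4.1.4.5, but for a full dose Section 4.1.4.4 still holds the infusion.
- *Day 8 shows the same contradiction.* The half dose on Day 8 lies outside the stated scope of Section 4.1.4.4, so the two rules do not meet there.

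**Conclusion.** The contradiction is real but narrow. It applies to full-dose infusions from Cycle 1 Day 15 onward, when a decline related to BI 836826 leaves platelets above 10,000 and below 25,000/µL on the infusion day. It rests on the absence of any rule of precedence and on the instruction to keep the schedule being read as written.

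Its main weight is on treatment consistency and safety for patients still receiving BI 836826. A reader might infer that it undermines the MTD data; the documents do not show that. Evaluability is at risk only at Cycle 1 Day 15 and only when recovery needs more than one week. Few such decisions can remain once recruitment has stopped. The frequency of infusion-day counts in the interval cannot be derived from the documents: such counts can occur, but no rate can be given.

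**What to change.** Reconcile Section 4.1.4.4 with the thrombocytopenia rows of Section 4.1.4.5, and state which of them governs whether a full-dose infusion is given on schedule. If the two are meant to be cumulative, say so in both places and word the table's schedule instruction to match. The clinical team must choose the rule; none is proposed here.

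Before the list of replaced patients in SAP Section 6.3 is finalised, check whether any Cycle 1 Day 15 decision involved a count in this interval, and report it if so.

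The cost is protocol wording and one look at existing blood counts. The model, the analysis sets and the sample size do not change.
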